#### Sample size:

The significance level (Alpha) will be 5%, power (1-beta) 80%. The composite major adverse event rate (all-cause mortality, AMI, cerebral vascular event, BARC type 3 or type 5) in the CR group was set at 4.19% based on the RIVAL study and with a non-inferiority cutoff of 1.89%. In the presence of a true difference in favor of the experimental group of 1.89%, the total population required is 2782 and 1391 patients per group to be 90% certain that the upper limit of the one-sided 95% confidence interval will exclude a difference in favor of the standard group of > 1.89%. The calculation of the final overall population with a 5% loss is 2922, 1461 patients per group.

In the Cath-lab at the Instituto Nacional de Cardiología Ignacio Chávez, 4608 procedures are performed per year, of which 3600 are in adults with ischemic and structural heart disease. Of this total group, 2880 are PCI. Approximately 90 procedures per month or 1080 per year correspond to patients with SICA; of these patients, approximately 65% (702) correspond to STEMI; thus, at least our institute would contribute 2106 patients for this multicenter study, which corresponds to 75% of the total population required; the rest of the centers should only contribute 766 patients. It is feasible to carry out the study over a period of 36 months.

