### Specification of the variables

Independent: distal and proximal radial access.

Dependent: age, gender, body weight, body mass index, diabetes mellitus, systemic arterial hypertension, smoking, chronic obstructive pulmonary disease, dyslipidemia, overall death, cardiovascular death, myocardial infarction, vascular complications, vascular access bleeding, stent thrombosis, new revascularization of the treated vessel, cerebral vascular event, radial artery thrombosis, culprit vessel, stent type, left ventricular ejection fraction, troponin levels, ECG ST segment changes, ECG T wave changes.

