## STATISTICAL ANALYSIS PLAN

The SPSS 2020 package will be used for the statistical analysis as described above. No interim analysis has been pre-specified. The analysis will be by treatment intention according to assignment. Categorical variables will be expressed as percentages, and continuous variables as means  $\pm$  standard deviation. To compare categorical variables, the chi-square test or Fisher's exact test will be used, and to compare continuous variables, the Student's t-test or Mann-Whitney U test will be used. Survival

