**Instituto Nacional de Cardiología Ignacio Chávez**

*Renacimiento de la Excelencia*

curves will be constructed using the Kaplan-Meier method. Conditional logistic regression models will be obtained to obtain OR and CI to establish the association of baseline patient characteristics and net adverse clinical events. The pre-specified subgroup for analysis is STEMI.

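### The only between-group method the SAP gives for a binary endpoint is unadjusted; a pre-specified standardised risk difference would be a small, cheap gain in precision.

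*Combined protocol and SAP*

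**What the plan says.** - **Between-group method.** The Statistical Analysis Plan has a general sentence beginning "To compare categorical variables, the chi-square test", with Fisher's exact test as the alternative. The analysis is by intention to treat. No analysis is labelled primary.
- **Models.** The same section, continued on the next page, plans Kaplan-Meier curves and conditional logistic regression giving odds ratios. The stated purpose of the regression is "to establish the association of baseline patient characteristics and net adverse clinical events". It does not say that the access arm enters the model, nor what the conditioning strata are.
- **Variables.** Specification of the variables has a list that opens "Dependent: age, gender, body weight, body mass index, diabetes mellitus, systemic arterial hypertension". The list mixes baseline characteristics with outcomes (death, infarction, stent thrombosis) and procedural items (stent type). It gives no measurement time for ejection fraction, troponin or ECG changes. Centre is not listed but is known for every patient.
- **Decision rule.** It appears only under Sample size: the event rate "in the CR group was set at 4.19% based on the RIVAL study", "with a non-inferiority cutoff of 1.89" percentage points, and a requirement on the "upper limit of the one-sided 95% confidence interval will exclude a difference" larger than that cutoff.
- **Randomization.** Computerised, with no stratification factors named.

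**The concern.** Non-inferiority is to be judged by whether an upper confidence limit for a risk difference lies below 1.89 points. Anything that legitimately narrows that interval helps the trial reach a clear answer. Prognostic baseline variables can do this. A logistic model averaged over the trial population (standardisation, or g-computation) still yields a marginal risk difference, so the estimand and the margin's scale do not change. A conditional odds ratio, the quantity the planned logistic models report, is a different estimand and cannot be set directly against 1.89 points.

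At stake is modest precision in a design with little slack, in a trial where one of five centres is expected to supply about three quarters of the patients and neither randomisation nor analysis is said to account for centre.

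**Working it through.** **Inputs from Sample size.** Control rate p = 0.0419; margin m = 0.0189; one-sided 5%; 80% power; 1391 per group, 2782 in total.

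**1. Reproduce the plan's figure.** With equal true rates and unpooled variance, n per group = 2p(1 − p)(z₀.₉₅ + z₀.₈₀)² / m².
- 2 × 0.0419 × 0.9581 = 0.08029
- (1.645 + 0.842)² = 6.183
- 0.08029 × 6.183 / 0.0189² = 1389.6, so 1390 per group against 1391 stated.

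The section also says "to be 90% certain", and it posits a true benefit of 1.89 points. Neither matches 1391: 90% power with equal rates needs 1925, and the benefit taken literally needs 271 (80%) or 376 (90%). A two-sided 5% superiority comparison of 4.19% with 2.30% at 80% power gives 1379, so the match at 1390 is close but not unique. These statements need reconciling. The base case here is equal rates, one-sided 5% and 80% power.

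**2. Unadjusted precision.** SE = √(0.08029 / 1391) = 0.760 points. The distance from estimate to upper limit is 1.645 × 0.760 = 1.250 points. Power = Φ(1.89/0.760 − 1.645) = Φ(2.488 − 1.645) = 80.0%.

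**3. What covariates could remove.** The documents give no c-statistic, so a range is assumed. Take a normally distributed risk score on the logit scale with standard deviation s, and set the intercept so that mean risk is 4.19%. The share of variance explained on the risk scale is R² = Var(risk) / [0.0419 × 0.9581]. The adjusted SE is the unadjusted SE × √(1 − R²), and the saving in patients is 1391 × R².

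| s | c-statistic (assumed) | R² | Half-width (points) | Power | Saving per group |
|---|---|---|---|---|---|
| none | none | 0 | 1.250 | 80.0% | 0 |
| 0.50 | 0.64 | 1.1% | 1.243 | 80.4% | 15 |
| 0.75 | 0.70 | 2.65% | 1.233 | 81.0% | 37 |
| 1.00 | 0.755 | 5.1% | 1.218 | 81.8% | 71 |

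Worked row: at R² = 0.0265, √(1 − 0.0265) = 0.9867; 2.488 / 0.9867 = 2.521; Φ(2.521 − 1.645) = 81.0%.

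These are ceilings, because they treat the risk score as known. A simulation that estimated the coefficients (2782 patients, three continuous covariates, four centre terms) gave variance reductions of 0.9% (simulation SE 0.3) and 2.4% (SE 0.4) for the first two rows. Those are slightly lower but within simulation error.

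**4. Can the model be fitted?** Expected events are 2782 × 0.0419 ≈ 117. Access, four centre terms, age, sex and diabetes make eight coefficients, about 15 events each. The plan expects 766 patients from the other four centres: if these are equal, 766/4 ≈ 191 patients and 191 × 0.0419 ≈ 8 events per centre. The chance of no events in one centre-by-arm cell of about 96 patients is 0.9581^96 ≈ 1.6%, and over eight such cells 1 − (1 − 0.016)^8 ≈ 12%. The figure 766 does not add up with the institute's 2106 to either stated total. Using 2782 − 2106 = 676 instead gives 169 patients and about 7 events per centre. Main-effect centre terms should usually fit, but a pooling rule is needed.

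**The case against.** The strongest reply is that this is a preference. An unadjusted risk difference is valid in a randomised trial, the sample size was computed for one, and an interval that shortens from 1.250 to about 1.24 or 1.23 points will rarely change a conclusion against 1.89. That stands, and it is why the point is a minor improvement.

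Other parts of the reply also stand:
- A reader might infer that the SAP names the chi-square or Fisher test as its primary analysis. It does not. The sentence is generic and no primary analysis is named. Silence about the access arm in the logistic models is likewise not a statement that it is left out.
- A reader might count the gain as free. The plan names only SPSS and Excel; standardisation needs a script, and covariates must be chosen in advance.
- Adjustment does not remove chance imbalance. It reduces the effect of imbalance in the modelled covariates only, and the unadjusted interval already allows for chance imbalance.
- At a c-statistic near 0.755 the 71 patients saved resemble the 70 per group added for losses (1461 − 1391). They do not offset the losses. The allowance is already in the total, and eliminating patients without 30-day follow-up raises a question of bias that precision cannot answer.

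A larger gap lies in the same place: the SAP does not specify the confidence limit on which the sample size rests, and a test of no difference does not test the margin. This does not defeat the point, because one edit can supply both the limit and the adjustment.

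**Conclusion.** The point holds as a small, inexpensive improvement. The only binary between-group method specified is unadjusted, no adjusted effect of access is planned, and usable baseline variables are recorded. For a model with only centre, age, sex and diabetes, the prudent expectation is the lower part of the range: at most about 1% to 3% less variance, and power of 80.4% to 81.0% instead of 80.0%. A c-statistic near 0.755 would give at most 81.8%, and nothing in the documents supports assuming it. The figures rest on assumed c-statistics, a 4.19% event rate in both arms, one-sided 5% and 1391 analysed per group. The documents do not support the stronger reading that the planned comparison is biased or invalid.

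**What to change.** Before outcome data are reviewed, amend the Statistical Analysis Plan to state that:
- the primary analysis is the 30-day risk difference (distal minus conventional) and its one-sided 95% upper limit, compared with the 1.89-point margin;
- it comes from a logistic model with allocated access, age, sex, diabetes and centre, standardised by g-computation, with a delta-method or bootstrap standard error;
- the covariate list is fixed in advance and limited to variables measured before access is attempted, so ejection fraction, troponin and ECG changes are left out unless shown to meet that condition;
- small centres are pooled by a stated rule when a centre has too few events;
- patients without a 30-day outcome are handled by a stated method, since standardising over everyone randomised predicts their outcomes under a missing-data assumption;
- the unadjusted risk difference with its upper limit is reported as a sensitivity analysis.

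The cost is a paragraph of SAP text, a short script beyond standard chi-square output and an early decision on covariates. No new data or patients are needed.

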**SALUD**  
SECRETARÍA DE SALUD

**Instituto Nacional de Cardiología Ignacio Chávez**

*Renacimiento de la Excelencia*

curves will be constructed using the Kaplan-Meier method. Conditional logistic regression models will be obtained to obtain OR and CI to establish the association of baseline patient characteristics and net adverse clinical events. The pre-specified subgroup for analysis is STEMI.

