### **OBJECTIVES**

Primary:

The primary objective is to compare the composite of adverse events of all-cause mortality, AMI, cerebral vascular events, BARC type 3 or type 5 (Bleeding Academic Research Consortium) at 30 days in patients with STEMI who received PCI via RDA versus CRA.

Secondary:

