**Instituto Nacional de Cardiología Ignacio Chávez**

*Renacimiento de la Excelencia*

To compare the composite of net adverse events of all-cause mortality, AMI, cerebral vascular events, urgent Revascularization of Treated Vessel, definite stent thrombosis, type 3 or 5 BARC at 30 days evolution in patients with STEMI who received PCI via RDA versus CRA.

To compare the rate of clinical adverse events individually at 30 days of evolution in patients with STEMI who received PCI via RDA versus CRA.

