## METHODOLOGY

Study design:

Prospective: Because of the temporality.

Randomized: For the assignment of the intervention.

Comparative: For the type of analysis.

Multicenter: Participation of 5 centers for patient recruitment.

\*Five centers in Mexico will participate, including the National Institute of Cardiology.

Description of the study population

Target population:

Patients with a diagnosis of STEMI who underwent PCI.

Eligible population:

Patients >18 years old, of both genders, with the diagnosis of STEMI undergoing PCI via RDA and CRA who are not in cardiogenic shock and have not previously undergone coronary revascularization surgical treatment.

Inclusion criteria:

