**Instituto Nacional de Cardiología Ignacio Chávez**  
*Renacimiento de la Excelencia*

Patients > 18 years old, with a diagnosis of STEMI undergoing PCI treatment at the Instituto Nacional de Cardiología Ignacio Chávez.

Patients with permeable radial artery in its proximal and distal segments.

Patients who agree to participate in the study and sign the informed consent form.

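### Do the whole-trial STEMI subgroup and the conditional logistic model with no named stratum require a change to the SAP?

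*Combined protocol and SAP*

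**What the plan says.** The last two sentences of the Statistical Analysis Plan are at issue.

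- **Regression.** "Conditional logistic regression models will be obtained to obtain OR and CI", to relate baseline characteristics to net adverse clinical events. No stratum, matched set or conditioning variable is given. The Randomization section says only that allocation is computerized, and Methodology mentions five centres without making centre a stratum.
- **Subgroup.** "The pre-specified subgroup for analysis is STEMI". No other subgroup is listed.

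The population is defined in Methodology. The target population is "Patients with a diagnosis of STEMI who underwent PCI", and the inclusion criterion is adults "with a diagnosis of STEMI undergoing PCI treatment". The recruitment estimate under Sample size counts the same patients: "approximately 65% (702) correspond to STEMI; thus, at least our institute would contribute 2106 patients for this multicenter study".

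There are two composites. The primary objective reads "The primary objective is to compare the composite of adverse events of all-cause mortality, AMI, cerebral vascular events" and adds BARC type 3 or 5 bleeding. The secondary objective is wider: "To compare the composite of net adverse events of all-cause mortality, AMI, cerebral vascular events, urgent Revascularization of Treated Vessel", and it also adds definite stent thrombosis. The Research Question and Hypothesis attach the label net adverse clinical event rate to the primary question.

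**The concern.** A pre-specified subgroup should divide the trial population so that the treatment effect can be compared across its levels. One that contains everybody allows no contrast and no interaction test. It also raises the suspicion that another subgroup was meant and lost in drafting; a replacement chosen after the data are seen could not be called pre-specified.

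The regression raises a different doubt. A conditional likelihood is defined only once the strata are known. With none named, two analysts could fit different models and both claim to follow the plan. The outcome label adds a further doubt, because the secondary objective uses a very similar phrase for a wider set of events. What is at stake is whether the table of baseline predictors can be reproduced from the plan.

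**Working it through.** **1. The subgroup.** The plan's accrual figure reproduces from STEMI patients alone: 1080 × 0.65 = 702 a year, and 702 × 3 = 2106. Research Question, Hypothesis, Objectives, target and eligible populations and inclusion criterion are all restricted to STEMI. The subgroup is therefore 2922 of 2922 planned patients, with 0 outside it. An analysis of it returns the overall result.

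**2. Number of events for the regression.** The stated sample size reproduces with control rate p = 0.0419, margin m = 0.0189, one-sided 5%, 80% power and no true difference:

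n = (1.645 + 0.842)² × 2p(1 − p)/m² = 6.18 × 0.0803/0.000357 ≈ 1390 per group (stated: 1391).

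- Equal rates: 2782 × 0.0419 = 116.6 events on the primary composite.
- The Sample size section also says "In the presence of a true difference in favor of the experimental group of 1.89" percent. That gives 1391 × (0.0419 + 0.0230) = 90.3 events. The stated size does not use this benefit, so 90 is kept only as a low case.

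The documents give no rate for the wider secondary composite.

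**3. Do the possible models differ?** Conditional and ordinary logistic regression part company when strata are many and small, as in matched pairs. Here no matching is described, and the only grouping in the documents is five centres.

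The check simulated 500 trials at each event count; 17 and 4 were skipped because a centre had no event. Assumed inputs: one centre of 2106; four of 169; centre log-odds offsets 0, −0.4, −0.2, 0.2 and 0.4; a binary covariate with 30% prevalence and true odds ratio 1.5.

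The figure 169 is (2782 − 2106)/4 = 676/4. The Sample size section instead gives 766 for the other centres, although 2106 + 766 = 2872 equals neither 2782 nor 2922. Using 766 would make those centres larger (766/4 = 191.5), which can only bring the two likelihoods closer.

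| Conditional on centre, compared with | SE ratio | OR ratio |
|---|---|---|
| Ordinary logistic, centre terms included | 0.999 (0.9985 to 0.9994) | 0.999 (0.998 to 1.001) |
| Ordinary logistic, no centre terms | mean 1.001 | mean 1.000 (0.957 to 1.047) |

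**4. Is the widest single-trial gap important?** On the log scale, ln 1.047 = 0.046 and −ln 0.957 = 0.044. For the standard error of the log odds ratio, the share of events among the exposed is about 0.30 × 1.5/(0.30 × 1.5 + 0.70) = 0.391.

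- 116.6 events split 45.6 and 71.0: √(1/45.6 + 1/71.0) = 0.190.
- 90.3 events split 35.3 and 55.0: √(1/35.3 + 1/55.0) = 0.216.

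The small non-event terms are left out; they would raise these values slightly. The largest gap is at most 0.046/0.190 = 0.24 of one standard error.

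**5. The outcome label.** The regression sentence uses the term found in the Research Question and Hypothesis, including the word clinical. The secondary objective's label lacks that word. The wording points to the primary composite.

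**The case for a change.** The strongest opposing case is that conditional might denote a variable-selection procedure rather than a stratified likelihood. That would matter. With nine candidate baseline variables, eight of them null and each tested at 5%, the chance of keeping at least one null variable is 1 − 0.95⁸ = 34%; with fourteen, thirteen of them null, it is 1 − 0.95¹³ = 49%. Odds ratios reported only after selection would also be too large on average. But the Statistical Analysis Plan mentions no selection, no entry or removal criterion and no stepwise procedure. It names a software package and says the models will give odds ratios and confidence intervals for associations. The selection reading has to be brought in from outside the documents, and its figures depend on an assumed candidate list and independent variables. It does not stand as a criticism of this plan.

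It can also be said that the clarification costs two sentences and would remove a choice made after the data are seen. The low cost is true. So are the underlying facts: the subgroup sentence is empty, and the stratum is unnamed. What is missing is a gain, because neither clarification would change a reported result to any practical extent. If a different subgroup was intended, only the sponsor can know; the documents hold no trace of one, and having no subgroup analysis is not an error.

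**Conclusion.** No change to the plan follows. The subgroup sentence is redundant and biases nothing. The unnamed stratum is a gap that analysts would fill sensibly: the two models the documents can support agree to about 0.1% on average, and by less than a quarter of a standard error in the most discrepant simulated trial. The outcome label is a small looseness whose natural reading is the primary composite. The effect is confined to the baseline-predictor table and does not reach the non-inferiority comparison.

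The subgroup conclusion rests on the text alone. The regression conclusion rests on the assumed centre sizes, offsets and covariate, on 90 to 117 primary-composite events, and on reading conditional as a stratified likelihood or as loose wording for ordinary logistic regression.

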**SALUD**  
SECRETARÍA DE SALUD

